9.0 ASSESSMENT OF SAFETY, ADVERSE EVENTS AND SERIOUS ADVERSE **EVENTS**

All subjects who receive study treatment will be assessed for safety.

ProQR Therapeutics Page 39 of 67 Investigators are responsible for monitoring the safety of subjects who have entered this study and for alerting the Sponsor regarding any event that seems unusual, even if this event may be considered an unanticipated benefit to the subject. The Investigator is responsible for appropriate medical care of subjects during the study and may add unscheduled visits, additional exams/tests for safety purposes.

9.1 Data Monitoring Committee

An independent DMC will provide safety oversight for the study. A DMC operational charter will be finalized, and an initial organizational meeting held prior to screening of the first subject.

Reference is also made to Sections 4.2.2 and 4.2.3.

9.2 Definitions of Adverse Event, Serious Adverse Event, and Suspected Unexpected Serious Adverse Event

9.2.1 Adverse Events

An AE is any untoward medical occurrence associated with the use of a drug in humans, whether considered drug related or not. Adverse events can include any unfavorable, noxious, unintended sign, symptom, or disease temporally associated with use of a study drug or other protocolimposed intervention, regardless of attribution. Adverse events may be spontaneously reported by the subject, discovered by Investigator questioning, or detected through laboratory test, or other means.

Adverse events include:

- Pre-existing medical conditions judged by the Investigator to have worsened in severity or frequency or changed in character during the protocol-specified AE reporting period (as specified in Section 9.4.1)
- Adverse events not previously observed in the subject that emerge during the protocol-specified AE reporting period (as specified in Section 9.4.1)
- Complications that occur as a result of protocol-mandated interventions
- Adverse events that occur prior to study treatment that are related to a protocol-mandated intervention (eg, invasive procedures such as blood draws, sedation prior to IVT injection)

9.2.2 Serious Adverse Events

An AE is considered "serious" if, in the view of Investigator, it results in any of the following outcomes:

Death

- Life-threatening AE. This definition implies that the subject, in the view of the Investigator, is at immediate risk of death from the event as it occurred. It does not include an event that, had it occurred in a more severe form, might have caused death
- Inpatient hospitalization or prolongs existing hospitalization, except for planned hospitalization
- Persistent or significant disability/incapacity (ie, the AE results in substantial disruption of the subject's ability to conduct normal life functions)
- Congenital anomaly or birth defect. This serious criterion applies if a congenital anomaly/birth defect is diagnosed in a child born to a female subject, or a female partner of a male subject exposed to the study drug
- Other important medical events. Medical and scientific judgment should determine whether an AE should be classified as serious in other situations, such as important medical events that may not be immediately life threatening or result in death or hospitalization but may jeopardize the subject or require intervention to prevent one of the outcomes listed in the definition above.

All AEs that do not meet any of the criteria for serious should be regarded as non-serious AEs. Surgery for lens opacity removal (lens replacement) is not considered a serious AE as it does not require the subject be admitted to a hospital unit based on the nature of the surgery. Even in the case where the subject may be hospitalized for convenience, or a subject is too frail to make the commute back and forth to the surgical center, it is still not a Serious AE. The terms "severe" and "serious" are not synonymous. Severity refers to the intensity of an AE (as in mild, moderate, or severe pain); the event itself may be of relatively minor medical significance (such as severe headache) (see Section 9.3.1). "Serious" is a regulatory definition and is based on subject or event outcome or action criteria usually associated with events that pose a threat to a subject's life or vital functions. Seriousness (not severity) serves as the guide for defining regulatory reporting obligations.

Severity and seriousness should be independently assessed when recording AEs and serious adverse events (SAEs) on the AE eCRF and SAE form.

9.2.3 **Suspected Unexpected Serious Adverse Reaction Definition**

In order to be qualified as a suspected unexpected serious adverse reaction (SUSAR), the AE must meet 3 criteria: the event is serious, there is a certain degree of probability that the event is a reaction to the study drug being researched and the nature and severity of the reaction are not in agreement with the product information (ie, the reaction is unexpected as per the reference safety information). All SUSARs will be reported as required to the Competent Authorities and to the Ethics Committee (EC)/Institutional Review Boards (IRBs) of the countries and centers concerned.

ProQR Therapeutics Page 41 of 67

9.2.4 **Adverse Events of Special Interest**

9.3 **Assessment of Adverse Events**

The Investigator is responsible for assessing the severity and causality of AEs.

9.3.1 **Assessment of Severity (Intensity) of Adverse Events**

On the AE eCRF, the Investigator will use the adjectives MILD, MODERATE, or SEVERE to describe the maximum intensity of the AE. For purposes of consistency, these intensity grades are defined as follows:

- MILD: Awareness of sign, symptom, or event, but easily tolerated. Does not interfere with subject's usual function.
- MODERATE: Discomfort enough to cause interference to some extent with subject's usual function and may warrant intervention.
- SEVERE: Incapacitating and interferes significantly with subject's usual function and warrants intervention.

ProQR Therapeutics Page 42 of 67 As described previously in Section 9.2.2, note the distinction between the severity and the seriousness of an AE. A severe event is not necessarily a serious event and may not meet the regulatory definition of serious. For example, a headache may be severe (interferes significantly with subject's usual function) but would not be classified as a serious AE unless it met one of the regulatory criteria for SAEs, listed above in Section 9.2.2.

Any change in severity should be noted in the eCRF, eg, a change from mild to severe or a change from severe to moderate should be noted with the start and stop dates for each intensity.

9.3.2 Assessment of the Relationship of Adverse Events to Study Drug

The Investigator will make a causality assessment about the relationship of each AE to study drug. Assessment of causality is based on considering associative connections (time or place), pharmacological explanations, previous knowledge of the study drug, presence of characteristic clinical or pathological phenomena, underlying conditions in the study population, exclusion of other causes, and/or absence of alternative explanations. To ensure consistency of AE and SAE causality assessments, Investigators should apply the following general guideline:

Not Related: The AE has an etiology other than the study drug (eg, preexisting medical condition, underlying disease, intercurrent illness, or concomitant medication); and/or the AE has no plausible temporal relationship to administration of the study drug (eg, cancer diagnosed 2 days after dose of study drug).

Related: An AE that is related to the study drug or its administration (ie, an event that follows a reasonable temporal sequence from administration of the study intervention, follows a known or expected response pattern to the suspected intervention, that could not be reasonably explained by the known characteristics of the subject's clinical state).

For all AEs and SAEs, Investigators will make separate assessments of causality about the relationship of the event to study drug and to study procedures (ie, IVT injection).

Note: The Investigator's assessment of causality for individual AE reports is part of the study documentation process and will be recorded in the subject's medical record, AE eCRF, and SAE form if applicable. Adverse events recorded without the Investigator's assessment of the relationship to study drug will be followed up until causality is assigned.

9.3.3 **Assessment of the Outcome of Adverse Events**

The Investigator will record the outcome of AEs and SAEs using the following criteria:

- Recovered/resolved: The subject has fully recovered from the event, with no residual effects observable.
- **Recovered/resolved with sequelae:** The subject has recovered from the event, but with residual sequelae effects observable.

ProQR Therapeutics Page 43 of 67

- **Not recovered/resolved:** Effects of the event are still present.
- **Recovering/resolving:** The subject has improved but has not fully recovered from the event.
- **Fatal:** The death is related to the event.
- **Unknown:** The outcome of the event is unknown to the reporter (eg, subject was lost to follow-up).

9.4 **Reporting of Adverse Events**

The Investigator is responsible for ensuring that all AEs and SAEs are recorded in the subject's medical record, AE eCRF, and/or SAE form, and reported to the Sponsor in accordance with protocol instructions. The AE eCRF can be used to report both AEs and SAEs. If necessary, eg, in case of failure of the Electronic Data Capture (EDC) system or for logistical reasons, a paper AESI/SAE/Special Situation reporting form may be used instead.

9.4.1 **Adverse Event Reporting Period**

After signing of the Informed Consent all significant medical conditions including signs/symptoms of the underlying disease and known pre-existing medical conditions found during the screening period and up to initiation of dosing will be captured as medical history. Any event/condition, including those related to participation in the study or study procedures, those not related to underlying disease or pre-existing medical conditions already part of medical history, and occurring before first dose of study treatment will be captured as a non-treatment emergent AE.

Any event/condition noted once the subject receives their dose of study drug will be captured as a treatment emergent AE. All AEs and SAEs regardless of attribution will be collected until at least 90 days following the last administration of study drug or the subject's EOS visit, whichever is later. At the last scheduled visit, the Investigator should instruct each subject to report to the Investigator any subsequent AEs/SAEs that the subject's personal physician believes could be related to prior study treatment.

SAEs unrelated to study treatment and non-serious AEs are to be followed until the last scheduled study visit (EOS visit), with the outcome at that point of time to be recorded in the eCRF. SAEs related to study treatment (Serious Adverse drug Reactions) are to be followed until resolution or until they return to baseline, stabilize, or the subject is lost to follow-up. Resolution of AEs and SAEs (with dates) should be documented on the AE eCRF and SAE form (if applicable) and in the subject's medical record to facilitate source data verification. For some SAEs, the Sponsor or its designee may follow up by telephone, facsimile, electronic mail, and/or a monitoring visit to obtain additional case details deemed necessary to appropriately evaluate the SAE report (eg, hospital discharge summary, consultant report, or autopsy report).

ProQR Therapeutics Page 44 of 67

9.4.2 **Eliciting Adverse Events**

A consistent methodology of non-directive questioning for eliciting AEs at all subject evaluation time points should be adopted. Examples of non-directive questions include:

"How have you felt since your last clinic visit?"

"Have you had any new or changed health problems since you were last here?"

9.4.3 **Recording Adverse Events and Serious Adverse Events**

Investigators should use correct medical terminology/concepts when recording AEs or SAEs on the eCRF and/or AESI/SAE/Special Situation reporting form. Colloquialisms and abbreviations should be avoided. Serious AEs must also be recorded on the AE eCRF or AESI/SAE/Special Situation reporting form. Only 1 medical concept should be recorded in the event field on the AE eCRF and AESI/SAE/Special Situation reporting form (if applicable).

Adverse Events Occurring Secondary to Other Events a.

In general, AEs occurring secondary to other events (eg, cascade events or clinical sequelae) should also be entered as separate AEs. For example, if severe diarrhea is known to have resulted in dehydration, both diarrhea and dehydration should be entered as AEs on the eCRF, and if also serious, as SAE on AE eCFR and AESI/SAE/Special Situation reporting form (if applicable).

b **Persistent or Recurrent Adverse Events**

A persistent AE is one that extends continuously, without resolution between subject evaluation time points. Such events should only be recorded once in the eCRF unless their severity increases. If a persistent AE becomes more severe or occurs more frequently, it should be recorded again on the AE eCRF with the increased severity grading.

A recurrent AE is one that occurs and resolves between subject evaluation time points and subsequently recurs. All recurrent AEs should be recorded individually on the AE eCRF.

Abnormal Laboratory Values c.

Only clinically significant laboratory abnormalities will be recorded as AEs on the eCRF and SAE form (if applicable).

If the laboratory abnormality can be characterized by a precise clinical term, the clinical term should be recorded as the AE or SAE. For example, an elevated serum potassium level of 7.0 mEq/L should be recorded as "hyperkalemia".

ProQR Therapeutics Page 45 of 67 Observations of the same clinically significant laboratory abnormality from visit to visit should not be repeatedly recorded as AEs on the eCRF and SAE form (if applicable), unless their severity, seriousness, or etiology changes.

d. **Deaths**

All deaths that occur during the protocol-specified AE reporting period (see Section 9.4.1), regardless of attribution, will be recorded on the AE eCRF and SAE form and reported to the Sponsor within 24 hours of event knowledge.

When recording a death, the event or condition that caused or contributed to the fatal outcome should be recorded as a single medical concept. For example, if death resulted from respiratory failure, the AE recorded should be "Respiratory Failure", and the outcome of the AE would be "Death". If the cause of death is unknown and cannot be ascertained at the time of reporting, record "unexplained death" on the AE eCRF and SAE form.

e. **Preexisting Medical Conditions**

A preexisting medical condition is one that is present at the start of the study. Such conditions should be recorded on the Medical History eCRF.

A preexisting medical condition should be recorded as an AE or SAE only if the frequency, severity, or character of the condition worsens during the study. When recording such events on an AE eCRF and SAE form (if applicable), it is important to convey the concept that the preexisting condition has changed by including applicable descriptors (eg, "more frequent headaches").

f. Hospitalization, Prolonged Hospitalization or Surgery

Any AE that results in hospitalization or prolonged hospitalization should be documented and reported as an SAE unless specifically instructed otherwise in this protocol.

g. **Pregnancy**

If a female subject or a female partner of a male subject becomes pregnant during study participation of the female subject or the male partner, a Pregnancy Report form should be completed and faxed to the Sponsor within 24 hours of learning of the pregnancy, using the fax numbers listed in the Study Reference Manual.

Abortion, whether therapeutic or spontaneous, will also be reported on a Pregnancy Report form and faxed to the Sponsor. Refer to the Study Reference Manual for forms and complementary reporting information. If the abortion meets seriousness criteria (see Section 9.2.2, Serious Adverse Event Definition), this information will be captured on the AE eCRF and SAE form (if applicable).

ProQR Therapeutics Page 46 of 67 Pregnancy should be followed up until after delivery, and any events to 3 months post-partum or termination of the pregnancy. Any congenital anomaly/birth defect in a child born to a female subject or to a female partner of a male subject exposed to the study drug should be recorded and reported as an SAE.

h. **Special Situations Reporting**

Medication errors and uses outside what is foreseen in the protocol, including overdose and occupational exposure must be reported to the Sponsor within 24 hours from awareness on an paper AESI/SAE/Special Situation reporting form (if applicable) for tracking purposes and will be considered a protocol deviation. Overdose is defined as any study drug dose administered above the intended dose for the cohort assignment. Additional instructions for reporting special situation information will be provided by the Sponsor at the time of notification.

9.5 **AESIs and Serious Adverse Events Notification**

For all AESI and SAEs, regardless of suspected causality, a completed AESI/SAE/Special Situation reporting form must be sent within 24 hours of discovery of the event to:

DRUG SAFETY

See Study Reference Manual

Any fatal or life-threatening (ie, imminent risk of death) event that is attributed by the Investigator to the study drug must be immediately telephoned to:

DRUG SAFETY

Phone: See Study Reference Manual for phone number

followed by submission of written case details on an AESI/SAE/Special Situation reporting form within 24 hours.

Serious AEs occurring any time after study participation that are considered by the Investigator to be possibly related to study drug must also be reported. The following are important points to remember when completing the SAE form:

- If complete information is not available, at a minimum, subject identifier, suspect drug, study center identifier, event or outcome, and Investigator assessment of causal relationship to study drug should be provided.
- A rationale for the causality assessment of an SAE should always be included, so that a better understanding of the event can be compiled.

ProQR Therapeutics Page 47 of 67

- Follow-up information, such as laboratory reports, discharge summaries, autopsy reports, and information concerning outcome of the event should be submitted by revising the SAE form as soon as the information becomes available. Copies of source documents, with subject identifiers redacted, should be submitted only when they are written in English. If source documents are not in English, the Investigator must summarize the source documents, providing a complete English narrative that includes a description of the events as it evolved, the results of all diagnostic procedures performed, treatments administered, and outcome of the event. A query regarding a follow-up report should be answered within 5 working days from receipt of the query.
- Appropriate diagnostic tests and therapeutic measures are to be performed as necessary and reported on the SAE form.
- All SAEs must be reported to the IRB/EC, if applicable. See the International Council for Harmonisation (ICH) GCP E6 (R2), Section 4.11.1 (ICH 2016).

9.6 **Expedited Reporting of Suspected Unexpected Serious Adverse Reactions**

- The Sponsor or its designee is responsible for notifying the study centers of all expedited SAEs that occur during any clinical studies that are using the study drug. The Sponsor or its designee shall also notify Central ECs and Central IRB of SUSARs or significant risks to subjects, per country requirements. All SUSARs will be reported as required to the Competent Authorities of all involved participating countries.
- The Investigator will notify local IRB/EC of SUSARs or significant risks to subjects, per local country requirements. The Investigator must keep copies of all AE information, including correspondence with the Sponsor or local IRB/EC on file.
- All studies that are conducted within any European country will comply with the European Clinical Trial Directive 2005/28/EC, the Clinical Trial Directive 2001/20/EC, and the Detailed Guidance CT-3 (2011/C 172/01) and Regulation 536/2014.

10.0 STATISTICAL METHODOLOGY

10.1 **General Considerations**

A comprehensive SAP specifies the statistical methodology, and table, listing and figure (TLF) formats for all aspects of the planned analyses. The SAP supports the completion of the Clinical Study Report (CSR) for this protocol. All AEs will be considered in determining the safety profile of QR-421a. Exploratory analyses not necessarily identified in the SAP may be performed to support the clinical development program. Any post-hoc, or unplanned, analyses not identified in the SAP will be clearly identified in the CSR, in accordance with applicable Standard Operating Procedures of the sponsor.

ProQR Therapeutics Page 48 of 67

10.2 **Determination of Sample Size**

This is a Phase 2/3 study designed to evaluate efficacy, safety, and tolerability of QR-421a in subjects with early to moderate vision loss.

10.3 **Randomization and Masking**

Subjects, treating physicians and study staff are masked. The physician administering study treatment will be unmasked to assignment of study drug or sham-procedure but will be masked to the dose of study drug.

The randomization procedure used to assign study treatment to eligible subjects will be through a centralized IWRS, utilizing the randomization schedule generated by the designated unmasked statistician. Subjects will be sequentially assigned according to a computer-generated randomization list in the appropriate randomization ratio to 1 of 3 treatment groups and the eligible eye will be treated accordingly (see Section 10.2 and Section 4.2). Stratification for baseline characteristics (when included) will be described in the SAP.

10.4 Replacement of Subjects

10.5 **Analysis Populations**

All Screened Subjects: All subjects who provided informed consent to participate in the study.

Intent to Treat Set: All subjects who were randomized.

Safety Set: All subjects who were randomized and received at least one dose of study treatment.

Full Analysis Set: All subjects who received at least one dose of study treatment and had at least 1 baseline observation or measurement. The Efficacy Evaluable Population will be defined

ProQR Therapeutics Page 49 of 67

separately for each endpoint, based on availability of at least 1 baseline measurement of that endpoint.

Per Protocol Efficacy Set: All subjects in the Efficacy Evaluable Population with the exception of subjects with major protocol deviations. The list of major protocol deviations selected for exclusion from this population will be completed prior to database lock. The Per Protocol Population will also be defined separately for each endpoint.

Systemic Exposure Population: All subjects who received QR-421a and who have measurable drug concentrations in blood samples.

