3.2 Secondary Objective

The secondary objectives of the study are:

- To evaluate the safety and tolerability of QR-421a
- To evaluate changes in Patient-Reported Outcome (PRO) measures in subjects treated with QR-421a
- To evaluate the systemic exposure of QR-421a

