4.1.2 Secondary Endpoints

The order in which the secondary endpoints will be analysed will be defined in the Statistical Analysis Plan (SAP).

Key Secondary Endpoint

• Ellipzoid Zone area (EZ) as measured by Spectral Domain optical coherence tomography SD-OCT

Other Secondary Endpoints

- Change from baseline in the following outcome measures:
 - o BCVA
 - Spectral domain optical coherence tomography (SD-OCT) (other measures)
 - Low Luminance Visual Acuity (LLVA)
 - Other measures of static perimetry
 - Full-field Stimulus Threshold (FST)
- Change from baseline in PRO measures, as assessed by:
 - Michigan Retinal Degeneration Questionnaire (MRDQ) (Lacy 2021)
 - o Patient Global Impressions of Severity (PGI-S)
 - o Patient Global Impressions of Change (PGI-C)
- Ocular and non-ocular adverse events (AEs)

Exposure of QR-421a in serum

4.1.3 **Exploratory Endpoints**

Change from baseline in mobility course score

4.2 **Study Design**

PQ-421a-004 is a double-masked, randomized, controlled, multiple-dose study to evaluate the efficacy, safety, and tolerability of QR-421a in subjects with RP due to mutations in exon 13 of the *USH2A* gene with early to moderate vision loss.

At study start subjects will be randomized to one of the following treatment groups:

- Group 1: QR-421a 180/60 µg (180 µg loading dose administered on Day 1, 60 µg maintenance dose administered at Month 3 and every 6 months thereafter; n = 40)
- Group 2: QR-421a 60/60 µg (60 µg loading dose administered on Day 1, 60 µg maintenance dose administered at Month 3 and every 6 months thereafter; n = 40)
- Group 3: Sham-procedure (administered on Day 1, Month 3 and every 6 months thereafter; n = 40)

The primary endpoint will be assessed at 12 months of treatment. Analysis of all other efficacy and safety parameters will also be reported at that time point. All efficacy and safety parameters will continue to be followed during the 24-month treatment period.

The same safety monitoring protocol and efficacy assessments will apply to both eyes.

ProQR Therapeutics Page 25 of 67

4.2.1 **Study Plan**

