Further details on the procedures for ophthalmic examinations are in the Study Reference Manual.

8.2.4 **Spectral Domain Optical Coherence Tomography**

Changes in SD-OCT findings, . All SD-OCT scans should be performed in accordance with the procedures outlined in the Imaging Procedure Manual.

8.3 **Systemic Exposure**

Blood samples for systemic exposure analysis of QR-421a will be collected from all subjects as indicated per the SOE-

8.4 **Immunogenicity**

Blood samples for assessment of immunogenicity will be taken as indicated per the SOE and stored for potential later quantification.

8.5 **Gene Sequencing**

A genotyping report (either historic or at screening) is required for eligibility. A blood or saliva sample for genotyping and gene sequencing should be obtained at or prior to the Screening Visit. In case the sample for gene sequencing analysis will be obtained prior to the first Screening Visit, a separate Informed

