10.11 Multiplicity Considerations

10.12 Subgroup Analyses

10.13 Systemic Exposure Analyses

Systemic exposure analyses will be performed as outlined in the SAP.

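### Do the measurable-only exposure set in the protocol and the lack of a serum concentration listing in the abbreviated SAP require a change?

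*Protocol*

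**What the plan says.** Protocol 3.2 gives as a secondary objective "To evaluate the systemic exposure of QR-421a", and Protocol 4.1.2 has the matching endpoint, "Exposure of QR-421a in serum". On sampling, Protocol 8.3 states "Blood samples for systemic exposure analysis of QR-421a will be collected from all subjects". Protocol 10.5 sets the analysis population as "All subjects who received QR-421a and who have measurable drug concentrations in blood samples"; the word measurable is not defined. Protocol 10.13 leaves the method open: "Systemic exposure analyses will be performed as outlined in the SAP".

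The abbreviated SAP of September 2022 has two populations (Section 3): All Screened Subjects, used for disposition, and the Safety Population, used for everything else. Section 4.7 has 19 listing items. Section 5 explains that the sponsor ended the study prematurely, rules out formal statistical analysis, limits tables to disposition, demographic and baseline characteristics and an adverse event overview, and keeps by-subject listings of raw data. Section 7 places the output shells in a separate list of planned outputs. The visible SAP text does not mention serum concentration or systemic exposure.

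**The concern.** There are two strands.

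The first is selection on the result. Every other set in Protocol 10.5 rests on consent, randomization, dosing, a baseline measurement or protocol deviations. The exposure set alone depends on the value of a post-dose measurement. Protocol 2.5 describes the intravitreal route as keeping systemic absorption low, so unquantifiable levels are plausible, and for an exposure objective they are informative. If treated subjects without a quantifiable level are removed, the mean exposure of the rest overstates that of all treated subjects, and every subject in the set is a detectable case.

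The second is reporting. Protocol 10.1 promises that "A comprehensive SAP specifies the statistical methodology, and table, listing and figure (TLF) formats for all aspects of the planned analyses", and 10.13 points to that document for exposure. A reader who then finds no concentration listing in SAP 4.7, and no sentence in SAP 5 setting exposure aside, could conclude that a secondary objective ends with neither data nor an explanation.

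**Working it through.** **1. Does any planned output use the set?** SAP 3 does not carry over the Systemic Exposure Population and assigns all data other than disposition to the Safety Population. The closed list of tables in SAP 5 contains no exposure table. The number of planned outputs that use the 10.5 definition is therefore 0. A concentration listing, if one is produced, would fall under the Safety Population rule and would show each subject's result, including those below the limit.

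**2. Which protocol endpoints have a listing in SAP 4.7?**

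| Protocol endpoint | Listing in SAP 4.7 |
|---|---|
| Static perimetry (primary; other measures secondary) | yes |
| EZ area and other SD-OCT measures | yes (SD-OCT) |
| BCVA, LLVA, FST | yes |
| MRDQ, PGI-S, PGI-C | yes |
| Ocular and non-ocular adverse events | yes |
| Serum exposure (secondary) | not named |
| Mobility course (exploratory) | not named |

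Of the 19 items, 0 name serum concentration. The laboratory item covers hematology, coagulation, chemistry and urinalysis only. Exposure is the one secondary endpoint without a listing, but not the one protocol endpoint without it: "Change from baseline in mobility course score" (Protocol 4.1.3) is also unlisted.

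**3. How large could the selection effect be if the set were used?** There is no figure in the documents to reproduce. Two inputs have to be assumed: f, the share of treated subjects removed, and r, their true mean as a fraction of the mean m of the measurable subjects. Then

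- all-treated mean = m × ((1 − f) + f × r)
- inflation = 1 / ((1 − f) + f × r), at most 1 / (1 − f) when r = 0

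With 2 × 40 = 80 subjects planned on QR-421a:

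| f (assumed) | Left in set | Inflation, r = 0.5 | Inflation, r = 0 |
|---|---|---|---|
| 0% | 80 | 1.00 | 1.00 |
| 5% | 76 | 1.03 | 1.05 |
| 10% | 72 | 1.05 | 1.11 |
| 25% | 60 | 1.14 | 1.33 |
| 50% | 40 | 1.33 | 2.00 |

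For example, at f = 25% and r = 0.5: 1 / (0.75 + 0.125) = 1.14.

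Three limits apply to this table.

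- It describes a mean that no section plans. The descriptive statistics in Protocol 10.8 are for efficacy endpoints, and 10.13 names no statistic.
- It treats each subject as one value. Membership in 10.5 is by subject, so someone with one measurable sample may be below the limit at other visits. The detectable proportion is 100% by construction only in the sense of ever detectable per subject, not by visit.
- If measurable means that a usable sample exists, nobody is removed because of the result and the inflation is 1.00.

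**4. What cannot be seen?** The list of planned outputs (SAP 7) is not among the documents. SAP 1.2, on study termination, opens by referring to a context that is missing from the text. Protocol 8.3 breaks off after its reference to the schedule of events. Any of these could hold the listing or the reason for leaving it out.

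**The case for a change.** The best case for a change rests on the reporting strand. The early stop explains why there is no exposure table, but not why there is no listing, since the primary endpoint and every other secondary endpoint keep theirs. Mobility is a weak parallel: it is exploratory and run at selected sites, whereas exposure is secondary and sampled in everyone. Protocol 8.4 also says "Blood samples for assessment of immunogenicity will be taken as indicated per the SOE and stored for potential later quantification", while the visible text of 8.3 has no such deferral, which suggests that exposure samples were meant to be assayed. If the omission was deliberate, SAP 5 is the natural place to say so, and one sentence or one listing would settle it.

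The textual facts in this stand. Exposure is the only secondary endpoint without a named listing, and SAP 5 gives a general reason for the reduced outputs rather than one for each item dropped.

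The inference is weaker. The contrast between 8.3 and 8.4 argues from silence in a paragraph that appears to be cut. SAP 1.2 calls the document abbreviated and limits it to what closing out the study requires, and SAP 5 gives the reason, so the reduction is declared even though it is not itemized. Naming each dropped item would be tidier, but it would change no result. Whether a listing is missing at all depends on an output list that cannot be examined here.

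**Conclusion.** No change to the plan follows. The definition in Protocol 10.5 is loosely worded, but it affects 0 planned outputs: the abbreviated SAP does not use the set and summarizes no exposure data. Changing it would alter no estimate, error rate or safety table. Were exposure ever summarized, an analyst would normally keep treated subjects with valid below-limit results, so the wording is a gap that ordinary practice fills. The range of 1.03 to 2.00 shows only what would happen under assumed shares of 5% to 50%; the documents support no particular value, and 1.00 is also possible.

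The missing listing is consistent with a close-out scope reduced after a premature stop. A query remains: whether the list of planned outputs contains a serum concentration listing. Looking at that list answers it.

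This conclusion assumes that the abbreviated SAP governs what is reported and that no exposure summary is planned outside its visible text. If one were, the first strand would need another look.
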